Profiling the vaginal and seminal microbiome and human virome in a smaller cohort of patients going through their first IVF cycle is an exploratory portion of this study. Existing studies are limited and conflicting regarding influence of the microbiome on IVF cycle outcomes.¹¹⁻¹³ This would be the first study to evaluate alterations in the reproductive tract microbiome across the IVF cycle in response to medications and supraphysiologic hormone levels, and the first to evaluate the human virome in this patient population.^{6,7} We would examine differences within and between groups and assess for the potential impact and association clinical outcomes of those patients exposed to prophylactic azithromycin, and those who are not. Optimizing the vaginal microbiome could serve as a potential target for therapy to help increase IVF success rates in the future with the goal of a full term, live birth.

C Study Objectives

C1 Primary Aim

Specific Aim 1: Determine the effect of withholding prophylactic antibiotic administration on clinical pregnancy rate (defined as a gestational sac, with fetal pole and cardiac activity, on ultrasound).

We *hypothesize* that withholding prophylactic antibiotics before embryo transfer will be non-inferior (absolute difference $\leq 15\%$) to routine prophylaxis in terms of clinical pregnancy rates.

C2 Secondary Aim

Specific Aim 2: Evaluate the impact of prophylactic antibiotic administration on miscarriage rate (pregnancy loss per clinical pregnancy) before 20 weeks.

Our *working hypothesis* is that miscarriage rates will be equivalent between the two groups.

Specific Aim 3: Determine the effect of no prophylactic antibiotic administration on embryo development.

We *hypothesize* that embryo development, as evaluated by fertilization rate (number of two-pronuclei embryos per mature oocyte), blastocyst conversion rate (number of day 5 embryos from two-pronuclei embryos), and blastocyst utilization rate (number of day 5 embryos transferred or frozen per two-pronuclei embryos) will be equivalent between the two groups.

Specific Aim 4: Determine the impact of prophylactic antibiotics or withholding prophylaxis on the vaginal and endometrial microbiome.

We *hypothesize* that azithromycin will impact the vaginal microbiome. Additionally, we expect to see changes across the IVF cycle that may be associated with cycle outcome endpoints.

Specific Aim 5: Evaluate the implications of the human virome on IVF outcomes.

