Couples will be randomized after providing written consent. Written consent will be obtained separately for both the male and female partner. In the case of same sex couples, only the female undergoing embryo transfer will be consented. Fifty couples going through their first IVF cycle enrolled in the noninferiority trial will also be offered enrollment in the pilot RCT and subsequently consented for the microbiome and virome profiling exploratory study. After consent, randomization in a 1:1 ratio to prophylactic antibiotics or no antibiotics will be performed in a block-randomized fashion per cycle number via computer random number generator. Couples randomized to the antibiotic group will receive the current standard regimen in our clinic: 1 gram azithromycin oral once for both partners the day controlled ovarian stimulation is initiated with injectable gonadotropins (IVF cycle start). In cases of same-sex couples, only the female undergoing the embryo transfer receives prophylaxis. Couples randomized to the no-antibiotic treatment group will not be prescribed oral antibiotic prophylaxis. Couples who agree to participate will have their charts marked indicating participation in the study. The couples' respective nurses will receive a message that will remain part of the electronic medical record regarding patient treatment group allocation so they can prescribe antibiotics appropriately. Embryologists who assess the embryo outcome measures will be blinded to patient treatment group allocation. The patients and their providers and nurses will not be blinded to treatment group allocation.

2.e Risks and Benefits

Potential problems with our study may be insufficient patient recruitment. The process of IVF is already stressful, time and user intensive and we will have to consent both

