partners. Patients may be hesitant to deviate from our previous standard of care. On the other hand, patients may want to avoid additional medication and may not take the antibiotic regardless to which arm they are randomized. We would mitigate this risk by a thorough informed consent and expressing our goal is to improve our current IVF protocols and that the best approach is not known while emphasizing the importance of compliance. Reportable severe events include development of pelvic infection following embryo transfer, a significant increase in spontaneous miscarriage rates or a note in increased contamination rates in the lab. Risks of pelvic infection in this low risk population following embryo transfer is remarkably rare as stated above and we do not anticipate this occurring. We anticipate miscarriage rates to be equivalent or improved in the non-prophylaxis group. The lab uses genatmicin routinely in embryo culture media to decrease contamination rates and will continue to be closely monitored for any increase in contamination rates. Reportable non-severe adverse events include yeast vaginitis, nausea and vomiting or other adverse reactions from antibiotic prophylaxis.

Obtaining a mid-vaginal swab poses little to no risk to the patient. The patient may experience some slight discomfort from one additional speculum exam at the time of baseline testing. The embryo transfer catheter tip will be sequenced for comparison to the vaginal swab following embryo transfer and will require no additional invasive testing or exams.

2.f Early Withdrawal of Subjects

While loss to follow up is extremely rare in this circumstance, some patients who are enrolled and randomized may not make it to egg retrieval or may not get an embryo transfer due to either a poor response to medications or poor embryo quality. We will account for these patients in our 5% drop out estimation and they will not be included in analysis.

2.g When and How to Withdraw Subjects

Patients can withdraw from the study at any time if they choose to do so. Their care will not be impacted by their participation or lack thereof.

2.h Data Collection and Follow-up for Withdrawn Subjects

Subjects who withdraw will not be included in the final data analysis.

D3 Study Drug –

3.a Description

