Intention-to-treat and per protocol analyses will be performed. Chi-squared and Fisher's exact tests will be used to compare categorical variables as appropriate. Kolmogorov-Smirnov test will be initially used to assess the distribution pattern of continuous variables. Normally distributed variables will be analyzed via Student's t-test. Non-normally distributed continuous variables will be analyzed with the Mann-Whitney U test. The primary analysis is based on difference in clinical pregnancy rate between the two groups. The sample size estimation for the study is based on this comparison with a non-inferiority approach as described above with an absolute difference of 15% or less to be considered non-inferior. Secondary analyses will include spontaneous miscarriage rate and embryo development. A subsequent interval analysis will assess live birth rate. Pearson's correlation coefficients will be used to quantify the association

between the two groups and embryo development. $P < 0.05$ will be considered statistically significant.

Each microbiota sample will have the taxon indicated as relative abundance. To assess the diversity across an IVF cycle, after log transformation, linear mixed regression will be applied. Wilcoxon rank sum will be used to measure for difference in richness and diversity with clinical outcomes of clinical pregnancy rate, miscarriage rate and embryo outcomes.

IBM® SPSS® statistics version 23 will be used for all analyses.

F5 Missing Outcome Data

All outcome data is required to be tracked by SART and no additional query will be required. We do not anticipate any issues with missing outcome data.

G Data Handling and Record Keeping

G1 Confidentiality and Security

Our practice is required to track patient demographic data and cycle outcome measures to report to the Society for Assisted Reproductive Technology (SART). Data is currently recorded and tracked through Research Electronic Data Capture (REDCap). REDCap is a secure web-based application designed to support data capture for research studies, providing 1) an intuitive interface for validated data entry; 2) audit trails for tracking data manipulation and export procedures; 3) automated export procedures for seamless data downloads to common statistical packages; and 4) procedures for importing data from external sources.¹⁸ Enrolled patients will be exported and tracked in a separate REDCap data set from our existing dataset.

G2 Records Retention

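### No planned embryo-development measure covers every randomised couple, so the Aim 3 rates can miss a loss of embryo yield

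*Combined protocol and SAP*

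**What the plan says.** F4 (Statistical Methods) promises intention-to-treat and per-protocol analyses and then says "Secondary analyses will include spontaneous miscarriage rate and embryo development". It gives no denominator, no unit of analysis and no rule for a zero denominator.

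The definitions are in C2, Specific Aim 3:

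- "fertilization rate (number of two-pronuclei embryos per mature oocyte"
- "blastocyst conversion rate (number of day 5 embryos from two-pronuclei embryos"
- "blastocyst utilization rate (number of day 5 embryos transferred or frozen per two-pronuclei embryos"

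The hypothesis is that these "will be equivalent between the two groups".

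On timing, section 2.d says "Couples will be randomized after providing written consent", and the antibiotic arm takes azithromycin on the day stimulation starts. Retrieval and fertilization come later.

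Section 2.f deals with randomised patients who do not reach egg retrieval or do not get a transfer because of poor response or poor embryo quality: "We will account for these patients in our 5% drop out estimation and they will not be included in analysis". F5 expects no problem with missing outcome data.

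Table 2 records the numbers of embryos transferred and frozen, maternal age and antral follicle count. It also lists the number of normally fertilized (2PN) oocytes among potential confounders.

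**The concern.** Each of the three rates divides by a quantity that treatment could have changed. Mature oocytes and 2PN embryos both arise after randomisation and after the drug is taken. For conversion and utilization the denominator is also the numerator of the fertilization rate, which Aim 3 itself treats as an outcome.

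Two things follow. A couple with no 2PN embryo has 0/0 for both blastocyst rates and drops out, although its embryo result is the worst possible. And if treatment affects fertilization, the 2PN embryos that remain in the two arms are differently selected, so the blastocyst rates are no longer a comparison protected by randomisation.

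Fertilization rate would normally be the safeguard, because it scores complete failure as 0%. Section 2.f takes that safeguard away by removing couples without a transfer. At stake is whether Aim 3 can support a statement that withholding azithromycin leaves embryo development unchanged for the couples who were randomised.

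**Working it through.** **1. The plan's own figures.** F1 gives a 41% clinical pregnancy rate, a 15-point margin, one-sided α = 0.025, 80% power and 5% drop-out. Per arm, n = (1.960 + 0.842)² × 2 × 0.41 × 0.59 / 0.15² = 168.8, so 169. Then 169 / 0.95 = 177.9, so 178 per arm and 356 in total. The stated size reproduces. Because 2.f counts couples without retrieval or transfer within the 5%, the plan allows for up to 178 − 169 = 9 such couples per arm. It gives no figure for any embryo outcome, so every embryo input below is an assumption.

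**2. Who contributes to each rate.**

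| Couple's course | Fertilization | Conversion and utilization | Under 2.f |
|---|---|---|---|
| No retrieval, or no mature oocyte | 0/0 | 0/0 | removed |
| Mature oocytes, no 2PN embryo | 0% | 0/0 | removed (nothing to transfer) |
| 2PN embryos, no transfer because of poor embryo quality | defined | defined, often low | removed |
| Transfer | defined | defined | kept |

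With 2.f as written, only the last row is analysed. Without 2.f, the first row is still undefined for all three rates. On either reading, no planned embryo measure covers all randomised couples.

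**3. Complete fertilization failure.** Assume 10 mature oocytes per couple; zero 2PN in 3% of couples in arm A and 10% in arm B; and in all other couples 7 2PN embryos and 50% conversion.

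- Conversion among couples with a defined rate: 50% in both arms.
- Blastocysts per couple: A = 0.97 × 7 × 0.50 = 3.395; B = 0.90 × 7 × 0.50 = 3.15. B is lower by 0.245, and 0.245 / 3.395 = 7.2%.
- Fertilization with failures scored 0%: A = 0.97 × 70% = 67.9%; B = 0.90 × 70% = 63.0%.
- Fertilization with 2.f applied: 70% in both arms.

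Of the three planned rates, only fertilization responds to the loss, and it does so only if 2.f is not applied.

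**4. Partial loss of fertilization.** Blastocysts per mature oocyte = fertilization rate × conversion rate. Assume 10 mature oocytes per couple.

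| | Fertilization | Conversion | Utilization | Blastocysts | Usable embryos |
|---|---|---|---|---|---|
| Arm A | 70% | 50% | 40% | 10 × 0.70 × 0.50 = 3.50 | 10 × 0.70 × 0.40 = 2.80 |
| Arm B | 55% | 58% | 46% | 10 × 0.55 × 0.58 = 3.19 | 10 × 0.55 × 0.46 = 2.53 |

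Both 2PN-based rates are higher in B while the yield is lower. Against A, blastocyst yield in B stays lower as long as conversion is below 0.70 × 0.50 / f, where f is fertilization in B: 53.8%, 58.3%, 63.6% and 70.0% for f = 65%, 60%, 55% and 50%.

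**5. How strong the effect might be.** A simulation assumed that a couple-level quality factor drives both fertilization and blastocyst formation, and that treatment lowers fertilization only.

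| | Arm A | Arm B |
|---|---|---|
| Fertilization | 66.9% | 55.0% |
| Couples with no 2PN embryo | 0.9% | 2.5% |
| Pooled conversion | 54.9% | 56.5% |
| Mean per-couple conversion | 50.2% | 50.6% |
| Blastocysts per couple | 3.67 | 3.11 |

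Yield falls by about 15% (3.11 / 3.67 = 0.85). Conversion barely moves.

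**The case against.** The best defence is that the three rates are meant to be read together. Fertilization rate is one of the listed Aim 3 outcomes and scores a complete failure as 0%. Multiplied by pooled conversion it gives blastocysts per mature oocyte. These are routine laboratory measures, and rates for different stages that differ do not contradict one another. Aim 3 asks about embryo development, which is not the same question as how many embryos a couple ends up with.

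Most of this stands, and it rules out replacing the prespecified rates. It does not close the gap, because 2.f as written takes the complete failures out of the fertilization rate too, and because mature oocytes are themselves a post-randomisation denominator.

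A reader might go further and infer that the blastocyst rates will move opposite to embryo yield, that the plan hides harm, or that Aim 3 can say nothing. The documents do not support that. Opposite movement appears in step 4 only because inputs were chosen to show it. In step 5, a 12-point loss of fertilization moved pooled conversion by only 1.6 points. In both steps the fertilization rate shows the loss plainly. A reader might also infer that only the two blastocyst rates are affected and that fertilization rate is free of the problem; it is not.

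**Conclusion.** The point holds as a low-cost improvement to a secondary aim. All three embryo rates are conditional on events after randomisation, two of them on another Aim 3 outcome. With 2.f in force, no planned embryo measure covers all randomised couples, which sits badly with F4's intention-to-treat statement. The rates can therefore miss a loss of embryo yield.

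How large a loss could be missed cannot be determined from the documents, and it may be small. The 7% and 15% differences above are illustrations from assumed inputs. The conclusion rests on two readings: that 2.f applies to Aim 3 as written, and that a couple with no 2PN embryo has no transfer. If 2.f were set aside, fertilization rate would capture complete failures among couples with mature oocytes, and the gap would narrow but not close. The primary analysis and the sample size of 356 are unaffected.

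**What to change.** - Keep the three rates as prespecified. Report the number of couples in each denominator by arm, and state how a zero denominator is handled.
- Add to F4 a comparison of usable embryos (transferred plus frozen) per randomised couple, counted as 0 when there are none. Use a negative-binomial or robust Poisson model over all randomised couples, with baseline age and antral follicle count as covariates.
- Amend 2.f so that its exclusion does not apply to this analysis.
- State that the count includes embryos of all culture days unless it is restricted to day 5. Table 2 does not limit the transferred and frozen counts to day 5, whereas the utilization rate in C2 does.
- Do not adjust for the 2PN count, although Table 2 lists it as a potential confounder. That would condition again on an outcome.

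The cost is a short addition to F4, an amendment to 2.f and one extra analysis. Table 2 already holds the data, and no visits or participants are added. The downside is precision: a per-couple count varies with ovarian response and is noisier than a rate, which the two baseline covariates can partly offset.

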As a smaller exploratory study within our RCT we aim to assess alterations and influence of the vaginal microbiome of women going through a fresh IVF cycles with a mid-vaginal swab at three time points in 50 women (25 in each arm): at the time of baseline testing, prior to egg retrieval and at the time of embryo transfer. Lastly we plan to obtain a swab at the time of embryo transfer to assess the human virome, which has never been described or evaluated in the IVF population.^{6,7} We will correlate our findings with the clinical outcomes we plan to track as a part of our primary study. We will consent and enroll the first 50 couples (25 in each arm) going through their first IVF cycle who enroll in the PAPET trial for the microbiome/virome study as well. The male partners of the women enrolled in the pilot RCT will also be enrolled in the pilot RCT. A small volume of the sample they produce at the time of *in vitro* fertilization will be obtained to evaluate the microbiome and virome in them in the same fashion.

B Background

B1 Prior Literature and Studies

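### F4 names a two-group test to relate microbiome diversity to embryo outcomes, but the embryo rates form no two groups and no grouping is given

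*Combined protocol and SAP*

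**What the plan says.** Section F4 gives one method for relating the microbiome to outcomes: "Wilcoxon rank sum will be used to measure for difference in richness and diversity with clinical outcomes". The list that completes the sentence is "clinical outcomes of clinical pregnancy rate, miscarriage rate and embryo outcomes".

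Specific Aim 3 in section C2 defines embryo development by three ratios. The first two are "fertilization rate (number of two-pronuclei embryos per mature oocyte), blastocyst conversion rate (number of day 5 embryos from two-pronuclei embryos"). The third, blastocyst utilization, sets the day 5 embryos that were used, whether by transfer or by freezing, against the same denominator as conversion. No section gives a threshold, category or other grouping for them.

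Section A3 describes the exploratory study as a "mid-vaginal swab at three time points in 50 women (25 in each arm"), and states its purpose: "We will correlate our findings with the clinical outcomes we plan to track as a part of our primary study".

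The other methods in F4 do not cover diversity against an embryo rate. Pearson correlation is assigned to the relation between trial group and embryo development. The linear mixed regression is for diversity across the cycle. The t-test and Mann-Whitney rules are again two-group comparisons. A P value below 0.05 "will be considered statistically significant", with no separate rule for the exploratory tests.

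**The concern.** The rank-sum test needs one variable that defines two groups and another that is ranked. With pregnancy or miscarriage as the group and diversity as the ranked variable, it fits. With a fertilization rate on one side and a diversity index on the other, neither variable defines groups, so the analysis cannot be carried out as written until somebody creates them.

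Two things are at stake. First, cutting a many-valued variable in two discards information, and the study has only 50 couples. Second, an unstated cut leaves a choice that can be made after the data are seen. There is already room for choice: three swab times, two measures (richness and diversity) and three embryo rates give 3 × 2 × 3 = 18 possible tests before any cut-point is picked.

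**Working it through.** **The plan's own figure.** The plan gives no power or precision figure for the exploratory analysis. Its only computed design figure is the main-trial size in F1, which reproduces. With 41% in both arms, a 15-point margin, one-sided alpha 0.025 and 80% power, n = (1.960 + 0.842)² × 2 × 0.41 × 0.59 / 0.15² = 168.8, so 169 per arm. Then 169 / 0.95 = 177.9, so 178 per arm and 356 in total. The present point does not depend on it.

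**Inputs.** From the documents: 50 women (A3), the rank-sum test and the 0.05 level (F4), and the three rates (C2). Assumed, because the documents are silent: where the cut falls, bivariate normality, the strength of correlation (rho), and two-sided testing.

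**Large-sample efficiency.**

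1. Splitting a normal variable at quantile q keeps φ(z_q)² / [q(1 − q)] of its information. At the median this is (1/2π) / 0.25 = 2/π = 0.637.
2. Ranking the other variable multiplies by 3/π, so the rank-sum test after a median split has efficiency (2/π)(3/π) = 6/π² = 0.608 against Pearson.
3. Spearman correlation has efficiency 9/π² = 0.912 against Pearson.
4. Rank-sum after a median split against Spearman: (6/π²) / (9/π²) = 0.667, and 50 × 0.667 = 33.3 couples.

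Under bivariate normality the argument is symmetric, so cutting the diversity measure instead costs the same.

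| Cut at | Rank-sum vs Spearman | Loss |
|---|---|---|
| one half | 0.667 | 33% |
| one third | 0.623 | 38% |
| one quarter | 0.564 | 44% |
| one fifth | 0.513 | 49% |

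**Dependence on the distribution.** For a uniform score, the squared correlation between the score and its median split is (1/8)² / [(1/12)(1/4)] = 0.75, so the split costs 25% instead of the 36% (1 − 0.637) for a normal score.

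**Simulated power at N = 50** (two-sided 5%, 20,000 bivariate normal data sets for each rho):

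| rho | Spearman | Rank-sum, median split | Rank-sum, quartile split |
|---|---|---|---|
| 0.3 | 52% | 37% | 31% |
| 0.4 | 79% | 61% | 51% |
| 0.5 | 95% | 82% | 74% |

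At rho = 0 all three reject in about 5% of data sets.

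Rates built from binomial counts (2,000 data sets per setting) behave the same way. At one assumed effect size, power for Spearman against rank-sum with a median split is 78% vs 63% with an average of 6 oocytes per couple, and 90% vs 76% with an average of 10. The oocyte numbers are also assumptions.

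**The case against.** The strongest reply is that the plan nowhere says it will dichotomise the embryo rates, and that the sentence in F4 is loose enough to allow other readings.

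- **Groups on the microbiome side.** Section B1 cites a study that contrasts Lactobacillus-dominated patients with others, and embryo rates could be compared between such groups. But F4 speaks of richness and diversity, gives no grouping of either, and a cut there loses information in the same way.
- **Groups by trial arm.** That would run, but it would not relate diversity to outcomes, which is what the sentence and A3 set out to do.
- **A natural yes/no embryo event**, such as any embryo frozen. Table 2 lists the number frozen, but no such binary outcome is defined.
- **The link to Aim 3 is inferred.** F4 says embryo outcomes in one place and embryo development in another, and C2 does not say whether the rates are computed per couple. The link is the natural one, since section D2 2.d uses a similar phrase for what the embryologists assess, but it is not stated.

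What stands is that a loss of information is not prescribed by the plan. A reader might infer that F4 forces a split of the rates and throws away a fixed third of the data. The documents do not support that: they contain no cut, no distribution and no effect size, and the cut could fall on either variable. A reader might also apply the familiar 2/π and conclude that 50 couples become about 32 (50 × 0.637 = 31.8). That figure counts only the split, and it matches neither the rank-sum test against Spearman (0.667) nor against Pearson (0.608).

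**Conclusion.** The point holds in a limited form. The method named in F4 does not fit embryo outcomes as Aim 3 defines them, and nothing else in the plan fills the gap. This is more than a missing detail, because on either reading that relates diversity to the rates the named test needs an unstated cut, and a better-fitting method is readily specified.

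The mismatch itself rests on no numerical assumption, only on reading embryo outcomes as the Aim 3 rates. The size does: about 67% of Spearman's information is kept (about 33 of 50 couples) if the cut is at the median and the data are bivariate normal. Uneven cuts keep less, and other distributions give other figures. Fifty is the enrolled number; D2 2.f expects some randomized couples not to reach retrieval or transfer, so fewer may be analysed.

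The importance is minor. The analysis is exploratory, carries no power claim, and uses a suitable test for two of its three listed outcomes. The primary comparison of clinical pregnancy rates is unaffected.

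**What to change.** Keep the rank-sum test for clinical pregnancy and miscarriage. For fertilization, blastocyst conversion and blastocyst utilization rates, add to F4 a method that uses the full scale and state:

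- **The measure.** Spearman correlation is the simplest choice. A binomial-type regression weighted by oocyte or embryo count is an alternative, and avoids giving a couple with very few oocytes the same weight as one with many.
- **Trial arm.** Combine within-arm estimates or include arm in the model, since Aim 4 expects azithromycin to alter the vaginal microbiome.
- **The swab.** Name one taken before the outcome is determined. Section E4 places the third swab just before embryo transfer, when fertilization is already settled; the baseline and pre-retrieval swabs precede all three rates.

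If the investigators do want a two-group comparison, they should state the grouping variable and its cut-point before looking at the data.

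The cost is a sentence or two in F4. No new data, visits or change in sample size are needed.
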